3.7 Fecal Bile Acid Analysis

Bile acids will be detected and quantified using liquid chromatography – mass spectrometry (LC-MS). Bile acids will be extracted from fecal material by sonication in acetonitrile, with the resulting extract injected directly into the LC-MS. All quantifications will be based on a C13 labeled internal standard and standard curves generated from known concentrations of each bile acid.

The investigator's lab will store all of the stool samples as well as the urine and blood samples collected for metabolomics. This laboratory is located at:

Wallin Medical Biosciences Building
University of Minnesota
[name]
[name]

3.8 Treatment Assignment

This is a randomized, open-label crossover study. Each participant will receive both dietary interventions. The sequence in which participants receive the interventions will be determined through computer-generated random number assignment prepared by the study statistician.

3.9 Withdrawal

3.9.1 Reasons for Withdrawal

A study participant will be discontinued from the study for:

- Completion of the study;
- Request by participant to terminate participation;
- Requirement for prohibited concomitant medication or treatment;
- Unable to comply with requirements of the protocol;
- Lost to follow-up;
- At the request of the institutional review board (IRB);
- The participant's well-being, based on the opinion of the investigator.

Participants who are discontinued from further study agent/interventions will be followed for safety until completion of the normal visit schedule. Participants will be contacted by phone within one week after withdrawal, and again after one month.

3.9.2 Handling of Withdrawal

Participants will be encouraged to complete the study; however, they may voluntarily withdraw at any time. The sponsor-investigator will provide a written explanation of the reason for

IRB#: 1610M97841

withdrawal in a source document and the reason will be recorded on a case report form. Participants will be asked for permission to continue scheduled evaluations, and complete an end-of-study evaluation. Medical care that may be required for management of adverse events in the course of the study will be charged to the medical insurance of the participant.

3.10 Study Termination

If the sponsor-investigator or appropriate regulatory officials discover conditions arising during the study that indicate that the study should be halted, this action may be taken after appropriate consultation between the sponsor-investigator, study statistician, and independent medical monitor. Conditions that may warrant termination of the study include, but are not limited to, the following:

- The discovery of an unexpected, serious, or unacceptable risk to the participants enrolled in the study,
- A decision on the part of the sponsor-investigator to suspend or discontinue testing or evaluation of the intervention.

4 STUDY PROCEDURES AND EVALUATION SCHEDULE

4.1 Clinical/Laboratory Evaluations and Study Schedule

Consent will be obtained before any clinical evaluations are performed. There is one screening visit and 6 visits planned over the approximately 1 month study duration for each subject. The study will last until every evaluable subject has completed the Safety Follow-Up Visit. (See Schedule of Events in the Appendices). Of note, Vital signs and collection of blood samples will be completed based on PI discretion, except for the Screening and Safety Follow-up Visit.

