3.4.2 Urine Samples

24-hour urine collections will take place per PI discretion at baseline (Day 0; Day 0±2 days), at the end of the first diet intervention (Day 7; Day 5±2 days), at the end of the washout period (Day 21; Day 19±2 days), and at the end of the second diet intervention (Day 28; Day 26±2 days). Participants will collect all urine for a 24-hour period in a collection bottle(s), which will be stored in the refrigerator. Participants will be asked to note the exact time they begin and complete their urine collection. The entire 24 hour sample (all urine containers) will be returned after completion of the 24-hour period. Samples collected will be used for urine sulfate analysis.

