3.4.3 Blood Samples

Blood (10 mL) will be collected per PI discretion in the clinic at visits 1, 2, 3, 4, 5, and 6 in Vacutainer Blood Collection Tubes. Blood for clinical laboratory assessment will be collected into tubes containing lithium heparin as anticoagulant. The tubes will be inverted carefully 3-5 times to mix blood and anticoagulant, and kept at room temperature until centrifugation, which will be done within 15 minutes of collection. Blood for measurement of TMAO and metabolites will be collected into a gel-barrier tube and allowed to clot for 30 minutes. Centrifugation of all samples will be carried out for 15 minutes at 1400 RCF (relative centrifugal force) at refrigerated temperature. The top layer (serum or plasma) will be collected and frozen at -80°C.

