6.3 Blinding

The clinical co-investigators will remain blinded to the intervention. Due to the nature of the intervention, the PI and other personnel giving dietary instructions, and participants will not be blinded. All investigators will be blinded to the randomization schedule and measured endpoints.

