27. Wilson KH. Efficiency of various bile salt preparations for stimulation of clostridium difficile spore germination. *J Clin Microbiol*. 1983;18(4):1017-1019.
29. Roediger WE. Decreased sulphur aminoacid intake in ulcerative colitis. *Lancet*. 1998;351(9115):1555.

13 Appendix 1. Schedule of Events

Procedures	Screening	Baseline	Visit 2	Visit 3	Visit 4	Visit 5	Visit 6
		0	Day 7	Day 14	Day 21	Day 28	Day 35
Obtain consent	X						
Medical history	X						
Vitals*	X	X	X	X	X	X	X
Height	X						
Weight	X	X	X	X	X	X	X
Clinical labs ^{1*}		X	X	X	X	X	X
Fasting blood for TMAO and metabolites*		X		X		X	X
Provide stool sample**		X	X	X	X	X	X
24-hour urine collection*		X	X	X		X	X
Diet assignment		X			X		
Dietary History Questionnaire		X					
Provide food diary	X	X	X	X	X	X	X
Review food diary		X	X	X	X	X	X
Adverse events/Concomitant medications		X	X	X	X	X	X

¹Clinical labs include: fasting lipid panel and C-reactive protein (CRP)

*Optional based on PI discretion

**Intermittent stool samples (in frozen collection tubes) will be dropped off at each respective visit following collection. Samples will be collected on days (± 2 days) -4, -2 3, 5, 9, 11, 16, 18, 23, 25, 30, and 32.

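### Blood and 24-hour urine are left to the discretion of a PI who knows the diet, with no rule for matching the two diet periods, so within-person pairs can be lost

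*Combined protocol and SAP*

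**What the plan says.** - **Section 4.1:** "Vital signs and collection of blood samples will be completed based on PI discretion, except for the Screening and Safety Follow-up Visit". This sentence covers vital signs and blood, not urine.
- **Section 3.4.3:** blood "will be collected per PI discretion in the clinic at visits 1, 2, 3, 4, 5, and 6". Visit 6 is the follow-up visit.
- **Section 3.4.2:** "24-hour urine collections will take place per PI discretion at baseline", and likewise at the ends of the first diet, the washout and the second diet. On purpose it says: "Samples collected will be used for urine sulfate analysis".
- **Appendix 1, Schedule of Events:** the rows for vitals, clinical labs, TMAO blood and 24-hour urine carry the footnote "Optional based on PI discretion". The stool row carries a different footnote, about the extra tube samples.
- **Section 6.3:** "Due to the nature of the intervention, the PI and other personnel giving dietary instructions, and participants will not be blinded". The next sentence adds: "All investigators will be blinded to the randomization schedule and measured endpoints".
- **Sections 2.5.3 and 6.1:** serum TMAO, carnitine and phosphatidylcholine are exploratory outcomes. Outcome measures at all levels are to be compared within and between diets by paired t-tests.

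No section says when the discretion should be used, ties the choice in one diet period to the choice in the other, asks for a reason when a sample is skipped, or gives a missing-data rule.

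**The concern.** A paired t-test uses only participants with both members of the pair, so one skipped collection removes that participant from the comparison. The person who may skip it knows the current diet. That person can also know about symptoms and adherence: investigators review the symptom log at each contact (section 3.3.1), and the PI assesses participants who do not keep to the diet (section 5.5).

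Two things are at stake. The first is the number of usable pairs in a small study meant to inform a larger one. The second is whether the remaining pairs represent all participants. Urine sulfate matters here even though section 2.5 does not list it. It could serve as an objective check on the diets, where the other evidence of adherence is diet records, study logs and dietitian contact.

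**Working it through.** **1. Inputs.** The plan has no figure to reproduce: section 6.1 says that no power calculation was done, and no collection rate is given. The sample size is 30 in the Protocol Summary, 15 in section 3, and 17 with 2 expected dropouts in section 6.1 (17 − 2 = 15). I use N = 15 and N = 30; the latter makes no allowance for dropout. The probability p that a discretionary sample is taken is assumed to be 0.9, 0.7 or 0.5.

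**2. Urine pairs if the choice is made at each visit.** Day 7 and Day 28 urine appear in section 3.4.2, the visit lists and the Schedule alike. With independent choices, expected complete pairs = N × p².

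| p | p² | N = 15 | N = 30 |
|---|---|---|---|
| 0.9 | 0.81 | 12.2 | 24.3 |
| 0.7 | 0.49 | 7.4 | 14.7 |
| 0.5 | 0.25 | 3.8 | 7.5 |

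**3. Urine pairs if the choice is made once per participant.** The retained share is then p itself: 90%, 70% or 50%. That is 13.5, 10.5 or 7.5 of 15, and 27, 21 or 15 of 30.

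**4. When lost pairs become bias.** Suppose collection depends on diet alone, say 0.9 on one diet and 0.5 on the other. Then 0.9 × 0.5 = 45% of pairs remain, but they are a random subset and the mean paired difference is unbiased. Bias needs a link to the difference itself. As an illustration, assume joint normality and that pairs are kept when a trigger, correlated ρ with the paired difference, exceeds a cut-off c that keeps a fraction k. The shift, in SDs of the difference, is ρ × φ(c) / k.
- ρ = 0: shift 0.
- ρ = 0.3, k = 0.9: 0.3 × 0.175 / 0.9 = 0.06 SD.
- ρ = 0.3, k = 0.5: 0.3 × 0.399 / 0.5 = 0.24 SD.

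Both ρ and k are assumptions.

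**5. TMAO.** The figures in steps 2 and 3 do not apply to it. The Schedule lists TMAO blood at Days 0, 14, 28 and 35 only. The lists for Visit 2 (Day 7) and Visit 4 (Day 21) agree: they include blood for clinical labs but not for research measurements. Under these lists nobody has an end-of-diet TMAO value on both diets, and neither period has both a start and an end value, even if every sample is taken. Section 3.4.3 could be read as TMAO blood at all six visits, so the sections need reconciling.

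**6. Other places that disagree.**
- Section 4.1 exempts Screening and the follow-up visit from discretion. Section 3.4.3 and the Schedule make Visit 6 blood optional, and neither section 4.2 nor the Schedule has screening blood. The Schedule also stars screening vitals.
- Section 3.4.2 has urine at Days 0, 7, 21 and 28. The visit lists and the Schedule have Days 0, 7, 14, 28 and 35, so the Day 21 baseline for the second period is absent there.

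**The case against.** This is a feasibility pilot with no power calculation. The serum outcomes are exploratory, urine sulfate is not a listed outcome, and optional sampling for such measures is a defensible use of resources. Nothing states that the choice is made at each visit: the visit-specific exceptions in section 4.1 point that way for vitals and blood, but a choice per participant or for the whole study is not excluded. All of this stands. It limits the weight of the point and is why both retention rates are shown.

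Three stronger readings are tempting, and the documents do not support them.
- **A reader might infer that the PI could select on laboratory results.** Section 6.3 blinds all investigators to measured endpoints, which limits that route. At Day 0 the first diet is only being assigned, so selection by diet is possible mainly from Visit 2 on.
- **A reader might infer that collection depending on diet biases the comparison by itself.** Step 4 of the working shows that it costs pairs. Bias needs a further link, for example through symptoms or adherence.
- **A reader might infer that the primary comparison is at risk.** Fecal gases and microbiota come from stool, which is outside this discretion.

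The objection does not supply a reason to leave the choice open between diet periods, because a rule that prevents selective loss costs almost nothing.

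**Conclusion.** The point holds as a modest, inexpensive improvement. The plan lets a PI who knows the diet decide, without criteria, whether blood and urine are taken, and nothing keeps the choice the same across diets. Under the assumed probabilities, 81% to 25% of Day 7/Day 28 urine pairs would survive choices made independently at each visit, and 90% to 50% would survive one choice per participant. The actual loss cannot be known from the documents. Bias is possible but conditional, and its size depends on a correlation that the plan gives no means to estimate. For TMAO, the listed sampling days are the larger problem: on the Schedule as it stands, the comparisons planned in section 6.1 have no matched values to use, whatever the PI decides.

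**What to change.** 1. In sections 3.4.2, 3.4.3 and 4.1 and the Schedule footnote, replace the open discretion with one recorded decision per participant on whether research blood, urine or both will be collected. Make it before the first diet is assigned at Visit 1. The Screening visit is a natural place, since the first urine kit is handed out there.
2. Where collection is chosen, take the samples at the same matched time points in both diet periods.
3. Record the reason for each omission and report completeness by diet and by sequence.
4. Reconcile section 4.1 with section 3.4.3 and the Schedule on Screening and Visit 6 blood.
5. Reconcile the TMAO blood days with the within-diet and between-diet comparisons in section 6.1.
6. Reconcile the urine days in section 3.4.2, Day 21 in particular, with the Visit 4 list and the Schedule.

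Items 1 to 3 cost a few sentences and a small loss of flexibility for the PI, who still chooses which participants are sampled. Items 4 to 6 are edits to the text; depending on how the days are settled, item 5 or 6 could add or move a collection for participants already chosen for sampling.

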4.2 Initial Screening Visit

The study will be explained to potential participants qualified from initial recruitment. Consent will be obtained at this time that will go over all the procedures and studies involved. During this visit the medical history will be collected and inclusion/exclusion criteria will be thoroughly reviewed. The following procedures will occur after the consent form is signed:

- Thorough review of the study, including involved procedures
- Medical history, including medications over the previous 12 months, and demographics
- Vital signs (heart rate, blood pressure, respiration rate)
- Height and weight measurement
- Review of methods used to record and measure food consumption during the study, to be conducted by dietitian.
- Three-day diet record is initiated following this visit, to be completed prior to visit 1 (baseline).
- Urine collection kit provided, to be completed prior to visit 1
- Link provided for web-based NCI Diet History Questionnaire III (DHQ III) to assess the baseline diet of subjects prior to entry into the study

4.3 Visit 1 - Baseline (Day 0)

The following procedures are conducted during this visit:

- Measurement of vital signs
- Weight measurement

- Collection of blood samples for clinical labs and research measurements
- Fecal sample collection
- 24-hour urine sample content collection
- Dietitian consult and review of 3-day diet record
- Assignment of first intervention diet, to begin immediately after conclusion of visit
- Receive instructions on completing adverse events diary card
- Review of adverse events and concomitant medications

4.4 Visit 2 (Day 7 ± 2 days; Final day of first diet intervention)

- Vital signs
- Weight
- Collection of blood samples for clinical labs
- Collection of stool sample for research measurements
- Review of 3-day diet record with dietitian
- Review of adverse events and concomitant medications
- 24-hour urine sample content collection
- Urine collection kit provided, to be completed prior to visit 3
- Review of adverse events and concomitant medications

4.5 Visit 3 (Day 14 ± 2 days)

- Vital signs
- Weight
- Collection of blood samples for clinical labs and research measurements
- Collection of stool sample for research measurements
- 24-hour urine sample content collection
- Review of 3-day diet record with dietitian
- Review of adverse events and concomitant medications

4.6 Visit 4 (Day 21 ± 2 days; First day of second diet intervention)

- Vital signs
- Weight
- Collection of blood samples for clinical labs
- Collection of stool sample for research measurements
- Assignment of second intervention diet, to begin immediately after conclusion of visit
- Review of 3-day diet record with dietitian
- Review of adverse events and concomitant medications
- Urine collection kit provided, to be completed prior to visit 5

4.7 Visit 5 (Day 28 ± 2 days; Final day of second diet intervention)

- Vital signs
- Weight
- Collection of blood samples for clinical labs and research measurements
- Collection of stool sample for research measurements
- 24-hour urine sample content collection

- Review of 3-day diet record with dietitian
- Review of adverse events and concomitant medications

4.8 Visit 6 (Day 35 ± 2 days; Follow-up visit)

- Vital signs
- Weight
- Collection of blood samples for clinical labs and research measurements
- Collection of stool sample for research measurements
- 24-hour urine sample content collection
- Review of 3-day diet record with dietitian
- Review of adverse events and concomitant medications

4.9 Unscheduled Visits

If at any time an unscheduled visit, including phone calls, should occur throughout the duration of the study, the following procedures will be completed:

- Adverse Events
- Concomitant medications
- Ask for any concerns about study procedures
- Physical examination and review of medical history as needed
- Order any lab tests as clinically indicated

4.10 Participant Compensation

Participants can receive up to a total of \$150 for participation in the study; \$25 paid for the completion of each study visit (a total of 6 study visits). Payment will be received in the form of gift cards.

4.11 Potential Risks

4.11.1 Risk of gastrointestinal symptoms

Changes in dietary intake can trigger gastrointestinal symptoms. However, these effects are typically minor in nature and occur in a small percentage of healthy volunteers.

4.12 Known Potential Benefits

IBD is a very complex condition and dietary intervention is only one component of a treatment and prevention plan. This study will generate information necessary to carry out a follow-up study specifically designed for patients with UC. We hope it will constitute an important step toward understanding the mechanisms of this disorder and contributions of diet and the gut microbiota to its pathophysiology. The potential benefits, therefore, are primarily societal in terms of enhancing understanding and ultimately finding better ways to treat this condition.

4.13 Risk/Benefit Ratio

Overall the risk of participating in this study is small. The benefit is primarily societal.

5 DATA SAFETY AND MONITORING PLAN

5.1 Definitions

Adverse Event (AE)

IRB#: 1610M97841

An adverse event (AE) is any symptom, sign, illness or experience that develops or worsens in severity during the course of the study. Intercurrent illnesses or injuries will be regarded as adverse events. Abnormal results of study procedures are considered to be AEs if the abnormality:

- Results in study withdrawal
- Is associated with a serious adverse event (SAE)
- Is associated with clinical signs or symptoms
- Leads to additional treatment or to further diagnostic tests
- Is considered by the Investigator to be of clinical significance.

Adverse Reaction

An adverse reaction is any adverse event caused by the investigational agent. Adverse reactions are a subset of suspected adverse reactions.

Suspected Adverse Reaction

A suspected adverse reaction is an adverse event for which there is a reasonable possibility that the investigational agent caused the adverse event.

Serious Adverse Event (SAE)

A serious adverse event (SAE) is any adverse event that is:

- Fatal
- Life-threatening
- Requires or prolongs a hospital stay
- Results in persistent or significant disability or incapacity
- A congenital anomaly or birth defect

Important medical events are events that may not be immediately life-threatening, but are clearly of major clinical significance and may be SAEs. They may jeopardize the subject, and may require intervention to prevent one or the other serious outcomes noted above.

Hospitalization

Hospitalization shall include any initial admission (even if less than 24 hours) to a healthcare facility as a result of a precipitating clinical adverse event; to include transfer within the hospital to an intensive care unit. Hospitalization or prolongation of hospitalization in the absence of a precipitating, clinical adverse event (e.g., for a preexisting condition not associated with a new adverse event or with a worsening of the preexisting condition; admission for a protocol-specified procedure) is not, in itself, a serious adverse effect.

Expected Adverse Event

Expected adverse events are those that are known to be associated with or have the potential to arise as a consequence of participation in the study.

Unexpected Adverse Event

An adverse event or suspected adverse reaction is considered unexpected if it is not listed in the Protocol at the specificity or severity that has been observed.

Unanticipated Problems Involving Risk to Subjects or Others (UPIRTSO)

An adverse event that in the opinion of the Principal Investigator is unexpected and related to the investigational agent.

Assessment of Severity

The sponsor-investigator will make an assessment of severity for each AE and SAE reported during the study. The assessment will be based on the sponsor-investigator's clinical judgment. The severity of each AE recorded will be assigned a severity based on Common Terminology Criteria for Adverse Events (CTCAE) grading.

Assessment of Causality

The sponsor-investigator will estimate the relationship between the investigational agent and the occurrence of each AE or SAE by using his best clinical judgment. Other elements, such as the history of the underlying disease, concomitant therapy, other risk factors, and the temporal relationship of the event to administration of the investigational agent, will be considered and investigated.

An SAE may be recorded when the sponsor-investigator has minimal information to include in the initial report. The sponsor-investigator may change his opinion of the causality in light of follow-up information, with subsequent amendment of the SAE report.

Categories	Definition
Definitely related	This relationship suggests that a definite causal relationship exists between the administration of the investigational agent and the AE, and other conditions (concurrent illness, progression/expression of disease state, or concurrent medication reaction) do not appear to explain the event.
Probably related	This relationship suggests that a reasonable temporal sequence of the event with investigational agent administration exists and, based upon the known or previously reported adverse reactions, or judgment based on the investigator's clinical experience, the association of the event with the investigational agent seems likely.
Possibly related	This relationship suggests that treatment with the investigational agent may have caused or contributed to the AE (i.e., the event follows a reasonable temporal sequence from the time of investigational agent administration and/or follows a known response pattern to the investigational agent but could also have been produced by other factors.)
Not related	This relationship suggests that there is no association between the investigational agent and the reported event.

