UPIRTSO	Unanticipated Problems Involving Risks to Subjects or Others

PROTOCOL SUMMARY

Title:	Dietary Impact on Intestinal Sulfate Metabolism
Phase:	1
Population:	30 healthy male and female volunteers. Subjects will be recruited from the Twin Cities metropolitan area and will participate as outpatients in this study.
Number of Sites:	1 (University of Minnesota)
Study Duration:	12 months
Subject Participation Duration:	Approximately 1 month
Agent or Intervention:	Dietary intervention will consist of following diets high in sulfur-containing amino acids (SAAs) and low in SAAs for 7 days each, with a 14-day washout period between interventions
Objectives:	The primary objectives of this proposal are to: 1) Compare low sulfur and high sulfur diets with respect to fecal production of hydrogen sulfide (H_2S) and other end products of microbial fermentation; and 2) Determine whether the diet alters the fecal microbiota and the relative proportion of fecal sulfate reducing bacteria.
Endpoints:	The primary endpoint is the change in H_2S concentration measured by gas chromatography. Comparisons will be made between the baseline measurement (Day 0) and end of intervention (Day 7) for each diet (within-group comparison) and between high- and low-sulfur diet H_2S concentration on Day 7 (between group comparison).

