5.2 Recording of Adverse Events

At each contact with the subject, the investigator will seek information on adverse events by specific questioning, reviewing the adverse events diary card, and, as appropriate, by examination. Information on all AEs will be recorded immediately in the source document and the appropriate AE module of the case report form (CRF). All clearly related signs, symptoms, and abnormal diagnostic procedures results will be recorded in the source document.

All AEs occurring during the study period will be recorded. The clinical course of each event will be followed until resolution, stabilization, or until it has been determined that the study treatment or participation is not the cause. AEs still unresolved at the conclusion of the study will be followed up on for one month. SAEs still ongoing at the end of the study period will be followed up to determine the final outcome. Any SAE that occurs after the study period and is

considered to be possibly related to the study treatment or study participation will be recorded and reported immediately.

Expected adverse events include:

- Events associated with venipunctures.
 - Discomfort and slight bruising.
- Events associated with dietary modification.
 - Changes in bowel habits, including diarrhea and/or constipation

Possible, although unlikely, adverse events that may be encountered include:

- Events associated with venipunctures.
 - Bruising
 - Bleeding
 - Lightheadedness, fainting
 - Infection at the venipuncture site
 - Nausea
 - Anxiety
 - Swelling at the venipuncture site

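### Section 5.1 judges UPIRTSO status and causality against the diets alone, so an unexpected serious event caused only by a study procedure falls outside the protocol's own trigger for an IRB report

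*Combined protocol and SAP*

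**What the plan says.** Section 5.1 defines a UPIRTSO as "An adverse event that in the opinion of the Principal Investigator is unexpected and related to the investigational agent". The causality rule in the same section asks the sponsor-investigator to judge each event against the investigational agent, and all four categories (definitely, probably, possibly, not related) are worded that way. The last one reads "This relationship suggests that there is no association between the investigational agent and the reported event".

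Section 5.1 does not define the agent. The row of the Protocol Summary headed Agent or Intervention reads "Dietary intervention will consist of following diets high in sulfur-containing amino acids (SAAs) and low in SAAs for 7 days each", so the agent is the pair of diets.

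Other safety text is wider. Section 5.1 describes expected events as those that can follow from taking part in the study. Section 5.2 follows events to resolution, to stabilization, or "until it has been determined that the study treatment or participation is not the cause". It also says that an SAE arising after the study period and "considered to be possibly related to the study treatment or study participation will be recorded and reported immediately". The same section lists venipuncture complications among the expected and possible events.

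Section 5.4.1 requires SAE reports to the IRB if the event falls under the UPIRTSO guidelines. Section 5.4.2 requires a report for UPIRTSO events.

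**The concern.** The protocol foresees harm from procedures, since it lists venipuncture events, but its causality scale has no place for that harm. UPIRTSO status requires relatedness to the agent, and the IRB-reporting clauses turn on UPIRTSO status. A serious event that the study plainly caused, but the diet did not, could therefore be filed as unrelated.

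At stake is whether staff who follow the protocol's own definitions would know that the IRB must be told. Data capture is not in question, because all adverse events are recorded under Section 5.2. Neither is any efficacy endpoint.

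**Working it through.** No arithmetic applies. The check sets the definitions side by side and runs a procedure-only event through them.

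1. *Scope of relatedness.* UPIRTSO definition (5.1): agent only. Causality rule and four categories (5.1): agent only. Expected events (5.1): participation. Follow-up of events (5.2): treatment or participation. SAEs after the study period (5.2): treatment or participation. The text that classifies an event is narrower than the text that governs its follow-up.

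2. *Can a procedure event be unexpected?* Yes. Under 5.1 an event is "considered unexpected if it is not listed in the Protocol at the specificity or severity that has been observed". A lasting nerve injury at the draw site is not listed in 5.2. Neither is a fracture after a faint, although fainting itself is listed.

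3. *Can it be serious?* Yes. One criterion in 5.1 is "Results in persistent or significant disability or incapacity", which a lasting nerve injury could meet. Hospital admission is another, which the fracture could meet.

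4. *Can it be related, as 5.1 uses the word?* Not if the procedure is the sole cause. Visit 1 shows this most clearly. Section 4.3 places a blood draw at that visit (at the PI's discretion under 3.4.3) and starts the first diet only once the visit is over. A faint at that draw leading to a fracture happens before any diet has been given, so no diet can have contributed. Only *not related* fits.

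5. *Result.* The event is unexpected and serious but not agent-related, so it is not a UPIRTSO under 5.1. By that definition neither 5.4.1 nor 5.4.2 requires an IRB report.

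6. *Does another section close the gap?*
   - The immediate-reporting clause in 5.2 covers only SAEs after the study period. A procedure-related SAE a week after the study would be caught, while the same SAE during the study has no matching clause.
   - Section 6.5 provides for review by the sponsor-investigator and an independent medical monitor. Its third and fourth stopping rules again require a link to the intervention or the study product.
   - Section 3.10 allows termination for a serious or unexpected risk of any origin.
   - None of these requires notice to the IRB.

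**The case against.** The strongest reply is that Sections 5.4.1 and 5.4.2 lean on outside requirements. They refer to UPIRTSO guidelines and to reporting timelines, yet the protocol states no timeline of its own. Section 9.1 also commits the study to federal human-subjects regulation and/or ICH E6. If the guidelines are an IRB policy that already covers procedures, the event would be reported whatever 5.1 says. This stands as a limit. A reader might infer from 5.1 that such events will go unreported, and the documents do not support that. They do contain a definition of UPIRTSO, however, and never say that another one overrides it.

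A second reply is that some procedure events can still be scored. The *possibly related* category accepts an event that "follows a reasonable temporal sequence from the time of investigational agent administration and/or follows a known response pattern to the investigational agent", with no cut-off in days. Fainting or nausea at a draw on the last day of a diet (Visits 2 and 5) could qualify, and a later draw is not strictly barred. This also stands. The gap is confined to events with no plausible dietary contribution.

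A reader might also try to size the gap by counting draws taken off diet. That would not measure it, because the gap depends on what caused the event and not on when the draw took place. A nerve injury from the needle is unrelated to diet at any visit. The number of draws is itself unsettled: Section 3.4.3 and Appendix 1 leave blood collection to the PI's discretion, while Section 4.1 excepts the Screening and Safety Follow-up Visit.

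Finally, the study is low-risk and the common venipuncture complications are already listed. That is right, and it governs the rating.

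**Conclusion.** The point holds as a minor correction to safety wording. Section 5.1 gives UPIRTSO and causality a scope narrower than the participation standard used elsewhere in 5.1 and in 5.2. Under the protocol's own definition, an unexpected in-study SAE caused only by a procedure would be rated *not related* and would not trigger an IRB report.

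This rests on two readings. The first is that the investigational agent means the diets, which the Protocol Summary supports although 5.1 does not say so. The second is that the 5.1 definition is the one applied in 5.4. If a wider IRB policy governs, the practical consequence disappears and only the inconsistency remains.

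The documents give no rate for serious procedure-related events, so no frequency is stated; such events should be rare. No endpoint or analysis is affected.

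**What to change.** In 5.1, define a UPIRTSO as an event that is unexpected and possibly, probably or definitely related to the assigned diet or to study procedures or participation. Word the causality rule and its four categories with the same scope, and record on the adverse-event form which source (diet or procedure) was judged related. In 5.4.1, state that reporting follows this definition or IRB policy, whichever is wider.

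The cost is a wording amendment to 5.1 and 5.4.1 and one added item on the form. The downside is a few more events to classify and possibly report.
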